5.1. Study Design Overview

This study is a Phase 3b, open-label, multicenter study to evaluate the efficacy and safety of oral ibrexafungerp in the treatment of subjects with complicated VVC episodes in subjects:

- not responsive to, or
- have isolates anticipated not to respond to, or
- who are refractory to or intolerant of fluconazole.

The susceptibility of historical isolates will be collected if available.

Approximately 150 eligible subjects will be enrolled. Subjects will be randomized to receive oral ibrexafungerp 300 mg administered twice a day (BID) for either one, three, or seven consecutive days, stratified by group based on *Candida* species and presence or absence of underlying medical conditions.

5.2. Study Schedule

The scheduled assessments will be carried out as described in Section 15 of the study protocol.

5.3. Randomization and Blinding

This is an open-label study. Subjects will be randomized to treatment, stratified by group based on the *Candida* species and presence or absence of underlying medical conditions.

5.4. Sample Size

This is an exploratory study, and no formal sample size calculation was performed. Approximately 150 subjects will be enrolled in allocation 50:50:50 in respect of 1, 3 and 7 days of treatment. Subjects will be randomized to treatment, stratified by group based on the *Candida* species and presence or absence of underlying conditions. The sample size of 150 is estimated to be adequate to perform an initial assessment of efficacy.

6. Statistical Analyses

6.1. General Considerations

All statistical processing will be performed using SAS® version 9.3 or later, unless otherwise stated. All statistical tests will be two-sided and interpreted at a 5% significance level.

The study is not powered for formal statistical comparisons. Descriptive statistics (i.e., mean, standard deviation, median, minimum, maximum, etc.) will be provided for all continuous variables; frequencies and percentages will be tabulated for incidence and categorical variables. For parameters measured over time, observed values and changes from baseline will be described for each time point.

The clinical cure and mycological eradication rates will be described by baseline Candida species, when the number of isolates per species allows.

All analyses will be presented by treatment group. Unless otherwise stated, data will be analyzed as it is with no imputation. No adjustment for multiplicity will be employed.

This Statistical Analysis Plan (SAP) will describe all statistical analyses in detail. The SAP will be finalized prior to database lock.

6.1.1. Baseline and Change from Baseline Definition

Baseline is defined as the last assessment prior to the first dose of study drug. If time and date are available, then the baseline assessment could be on the same day as first dose so long as it's before the time of first dose. If time is not available, the date prior to first dose will need to be used. Change from baseline is defined as: non-missing post- baseline value – baseline value. Baseline values will be re-calculated in Cycle 2 for QOL scale, VVS composite score, physical examinations, lab results and vital signs. If above baseline value is not available in Cycle 2, then use the last available value in Cycle 1 as baseline for Cycle 2.

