10.1.1.1. Screening (Day -2)

At Screening, subjects who are experiencing vulvovaginal symptoms will be evaluated by the investigator, who will obtain a vaginal sample for potassium hydroxide (KOH) testing and vaginal pH determination by the local laboratory prior to randomization and initiation of treatment. The vaginal samples will also be evaluated locally for findings indicative of bacterial vaginosis and *Trichomonas vaginalis* (WET Mount and/or DNA probe). If the investigator suspects *Herpes* virus, *Neisseria gonorrhoeae* or *Chlamydia trachomatis* infection, a vaginal sample will be collected and sent to a qualified local laboratory. A vaginal sample for fungal culture and for species identification and susceptibility testing will be obtained and sent to a designated central laboratory. The investigators and the subjects will rate the signs and symptoms of infection, respectively, on the VSS Scale (see Appendix 2). Safety procedures, including an abbreviated physical exam, vaginal exam, vital signs, laboratory tests and a pregnancy test will also be performed.

To be eligible for inclusion, subjects must have a minimum composite score of vulvovaginal signs and symptoms ≥ 4 with at least 2 signs or symptoms having a score of 2 (moderate) or greater in the VSS Scale at Baseline, a positive KOH test, a normal vaginal pH (≤ 4.5) and confirmed absence of other vaginal co-infections.

The Screening and Baseline (Day 1) visits may occur on the same day.

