14.8. Rating of Vulvovaginal Symptoms by the Subject Using the VSS Scale

Subjects will be asked to rate their vulvovaginal symptoms at Screening, Baseline (Day 1), during telephone interviews on Days 3, 5 and 7, at the TOC visit and at the FU visits.

Subjects will also assess their symptoms at unscheduled visits, as needed.

If the subject experiences persistence or worsening or recurrence of symptoms that per the investigator's assessment (e.g. symptoms ≥ 4) warrant the use of rescue antifungal therapy, the rating of the symptoms that led to the use of rescue antifungal therapy must be documented in the eCRF and a vaginal examination with rating of signs by the investigator should be completed. If the investigator's rating of the vulvovaginal signs and vaginal samples collection are not possible prior to the initiation of the rescue therapy, they should still be completed as soon as possible after rescue therapy is initiated.

Subjects will rate their symptoms of infection using the VSS Scale, where each vulvovaginal symptom will be given a numerical rating based on severity, as follows:

- Itching: absent = 0; mild = 1; moderate = 2; severe = 3
- Burning: absent = 0; mild = 1; moderate = 2; severe = 3
- Irritation: absent = 0; mild = 1; moderate = 2; severe = 3

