14.11. Rating of Vulvovaginal Signs by the Investigator Using the VSS Scale

The investigator (or qualified designee) will perform vulvovaginal examinations to rate the subject's signs of infection at the Screening, TOC and first FU visits at 14 days after EOT. The vulvovaginal examination will be repeated at the rest of the FU visits only if the subject presents with symptoms. Otherwise, no additional vulvovaginal examination will be conducted, or signs rated. Vulvovaginal examinations may be conducted at unscheduled visits, if needed.

If the subject experiences persistence or worsening or recurrence of symptoms that per the investigator's assessment (e.g. symptoms ≥ 4) warrant the use of rescue antifungal therapy, the subject may be enrolled into Treatment Cycle 2 and receive additional treatment with ibrexafungerp for a period up to 14 days as recommended by the investigator and following discussion with the sponsor.

Whether or not a subject enters Treatment Cycle 2, or be prescribed rescue therapy, a vaginal examination with rating of signs by the investigator should be completed prior to initiation of rescue therapy. If the investigator's rating of the vulvovaginal signs is not possible prior to the initiation of the rescue therapy, it should still be completed as soon as possible after rescue therapy is initiated.

Investigators will assess the signs of infection using the VSS Scale provided in Section 21 [Appendix 2]), a standardized, predefined scale where each sign of the vagina and/or vulva will be given a numerical rating based on severity, as follows:

- Edema: absent = 0; mild = 1; moderate = 2; severe = 3
- Erythema: absent = 0; mild = 1; moderate = 2; severe = 3
- Excoriation or fissures: absent = 0; mild = 1; moderate = 2; severe = 3

Other findings will be recorded using the most relevant medical term in the abbreviated physical examination page of the eCRF.

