14.12. Quality of Life (QOL) Questionnaire

Subjects will complete a QOL questionnaire at Baseline, TOC and at the follow-up visits.

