14.15. Study Drug Dosing

Treatment Cycle 1 applicable to all subjects: The first study drug dose (Day 1) will be administered at the clinical research center and the subsequent dose(s) will be self-administered by the subjects at approximately 12 ± 3 -hour intervals at home.

NOTE: If administering the first dose at the study center would complicate the administration of the second dose 12 hours later (e.g. first dose at 3 p.m. will require second dose at 3 a.m.), the subject can self-administer both Day 1 doses at home to allow for a more convenient dosing schedule (e.g., 8 p.m. and 8 a.m.). Details of study treatment groups and dietary requirements for treatment administration are provided in Section 12.1 and Section 12.2, respectively.

Treatment Cycle 2: A second treatment cycle will be allowed for subjects who did not achieve sufficient clinical improvement (e.g. VSS remains ≥ 3) on the randomized treatment (Cycle 1) as evaluated at the TOC and FU1 visits. A second treatment cycle will also be allowed for subjects with clinical cure/improvement/success who experience a recurrence before the last FU visit.

During Cycle 2, subjects may receive additional treatment with ibrexafungerp for a period up to 14 days as recommended by the investigator and following discussion with the sponsor.

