18.3. Subject Disposition, Discontinuation, and Baseline Data

Subject disposition in terms of the number and percentage of subjects enrolled by site will be tabulated. The number of subjects enrolled, number completing the study, and reasons for discontinuation will be summarized by treatment group. Subject demographics and baseline characteristics such as age, race, ethnicity, sex, weight, height, body mass index, region (if applicable) and other relevant parameters will be tabulated by treatment group.

Baseline is defined as the last non-missing assessment prior to the date (and time if appropriate) of the first dose of study drug. Change from baseline is defined as: post- baseline value – baseline value.

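### When clock time is missing, SAP 6.1.1 leaves Day 1 QOL, and VSS, laboratory and vital-sign values from same-day Screening/Baseline, without a Cycle 1 baseline

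*SAP*

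**What the plan says.** SAP 6.1.1 defines baseline as the last assessment before the first dose and then gives two branches. With a recorded time, a value from the dosing day may serve if it was taken ahead of the dose. Without one, "If time is not available, the date prior to first dose will need to be used". Protocol 18.3 is similar: "Baseline is defined as the last non-missing assessment prior to the date (and time if appropriate) of the first dose of study drug".

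The schedule against which the rule operates is as follows.

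- **Dosing.** Protocol 14.15: "The first study drug dose (Day 1) will be administered at the clinical research center". The same section lets a subject take both Day 1 doses at home if the clinic timing is awkward.
- **QOL.** Protocol 14.12: "Subjects will complete a QOL questionnaire at Baseline, TOC and at the follow-up visits". There is no Screening questionnaire.
- **VSS symptoms.** Protocol 14.8: "Subjects will be asked to rate their vulvovaginal symptoms at Screening, Baseline (Day 1), during telephone interviews on Days 3, 5 and 7". Later visits follow.
- **VSS signs.** Protocol 14.11 has the investigator rate "signs of infection at the Screening, TOC and first FU visits at 14 days after EOT". Screening is the only scheduled rating before dosing.
- **Safety laboratory tests.** Screening is the only scheduled sample before dosing (Protocol 14.7).
- **Vital signs.** Screening in Protocol 14.17; Table 1 also marks Baseline.
- **Visit timing.** Protocol 10.1.1.1: "The Screening and Baseline (Day 1) visits may occur on the same day".

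SAP 6.3.3 lists the Day 1 QOL questionnaire among the baseline characteristics. SAP 6.1.2 rules out imputation unless specified, and its date rules cover only adverse events and concomitant medications.

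**The concern.** The second branch of the rule requires an earlier calendar date for every measure, but some measures have no earlier date in the schedule. QOL never has one. VSS, laboratory tests and vital signs have none when Screening and Baseline coincide. Where time is missing, the rule therefore does more than choose a cautious baseline: it can leave none at all. Many of the values it rejects were taken before dosing by design. The VSS score, for example, is an eligibility criterion.

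Several planned analyses need a Cycle 1 baseline:

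- clinical success, defined as at least a 50% reduction in VSS;
- VSS change and the t-test of 3 against 7 days in Group B (SAP 6.4.1.2);
- QOL change, the main measure for the exploratory objective (SAP 6.4.3.2);
- laboratory change and shift tables, whose denominator requires a non-missing baseline (SAP 6.6.2);
- vital-sign change (Protocol 18.7.2).

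The SAP also contradicts itself. The same untimed Day 1 QOL score would appear as baseline in the demographic table and be refused as baseline for the change score. An analyst who overrides the rule to avoid this would be making an undocumented choice in an open-label study.

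**Working it through.** The plan states no figure for this point, so the check applies the rule to the schedule.

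**Rule (SAP 6.1.1).** A value qualifies if its date is before the first-dose date, or if it has the same date and a known time earlier than the dose. The latest qualifying value is the baseline.

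**Inputs.** First dose on Day 1. Screening on Day -2 when visits are separate, or Day 1 when they coincide. Pre-dose collection points are as listed above.

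**Result: day of the value that serves as Cycle 1 baseline.**

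| Measure | Separate days, time known | Separate days, time missing | Same day, time known | Same day, time missing |
|---|---|---|---|---|
| QOL | Day 1 | none | Day 1 | none |
| VSS symptoms | Day 1 | Day -2 | Day 1 | none |
| VSS signs | Day -2 | Day -2 | Day 1 | none |
| Laboratory tests | Day -2 | Day -2 | Day 1 | none |
| Vital signs (Table 1) | Day 1 | Day -2 | Day 1 | none |
| Vital signs (Protocol 14.17) | Day -2 | Day -2 | Day 1 | none |

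With times recorded, every measure has a baseline in both layouts. With times missing, QOL fails in both layouts and everything else fails only in the same-day layout.

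**Is there a rescue for Cycle 1?** Protocol 18.3 also works from the date and brings in time only where appropriate, so it does not admit an untimed Day 1 value. SAP 6.1.2 does not address assessment times. Protocol 18.4 assigns failure to subjects without a TOC assessment and does not deal with a missing baseline. The SAP 6.1.1 fallback to the last available Cycle 1 value applies to Cycle 2 only.

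**Size.** The documents give neither the share of records without a time nor the share of subjects entering on one day. With about 150 subjects planned:

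- QOL baselines lost = 150 × share of QOL records without a usable time. The range is 0 to 150.
- VSS, laboratory or vital-sign baselines lost = 150 × same-day share × share of those without a usable time. If, as an upper bound, none of the same-day records carries a time, assumed same-day shares of 0%, 25%, 50% and 100% give 0, 37.5 (about 38), 75 and 150 subjects.

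These are bounds and illustrations, not estimates.

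**The case against.** The strongest reply is that the harm depends on a document not available here. The SAP rests on CRF version 1.2. If that form records times for the assessments and the first dose, the first branch of the rule works and nothing is lost. This stands, and it means that no frequency can be claimed. It does not make the second branch correct: that branch was written for untimed records and gives the wrong answer for them in the cases above.

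A second reply is that requiring an earlier date is a reasonable caution when order cannot be verified. This has partial force. Screening procedures must precede dosing because eligibility depends on them. For QOL, the order follows only from the sequence of the narrative in Protocol 10.1.1.2. For the Day 1 symptom rating and the Table 1 Baseline vital signs, no order relative to the dose is stated. Caution is defensible for those items, but less so where it leaves no baseline at all.

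A third reply is that intent is clear from the opening sentence of SAP 6.1.1 and from SAP 6.3.3, so an analyst would probably use Day 1 QOL anyway. Probably so, but the specific sentence says otherwise and should not be left to be overridden informally.

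A reader might infer more than the documents support:

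- **That the QOL objective fails for the whole trial.** This would need every QOL time to be missing. Even then, observed scores by visit and the two global-impression items remain.
- **That the losses are selective by site.** Nothing in the documents describes same-day entry as a site practice.
- **That the main efficacy result is at risk.** Clinical cure is a VSS of 0 at TOC with no further antifungal therapy required, and it uses no baseline value.

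**Conclusion.** The concern holds for Cycle 1, conditional on missing time. As written, SAP 6.1.1 gives an untimed Day 1 QOL record no baseline, in conflict with SAP 6.3.3. It also gives no baseline to untimed VSS, laboratory and vital-sign values when Screening and Baseline share a date. Secondary, exploratory and safety analyses of change are exposed; the primary endpoint is unaffected. Subjects with separate-day visits keep a Screening baseline for VSS, laboratory tests and vital signs, and the Cycle 2 fallback avoids a missing baseline there.

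The number affected is unknown and may be zero. The conclusion assumes that the first dose falls on the date of the Baseline visit. If a subject dosing at home took it on a later calendar date, her untimed visit values would qualify. The home-dosing example in Protocol 14.15, with a first dose at 8 p.m., is still Day 1.

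This should be corrected because the rule is wrong whenever it is triggered in these cases and the correction is cheap, not because a large loss has been shown.

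**What to change.** Replace the sentence in SAP 6.1.1 on unavailable times with:

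> If time is missing, Screening (V1) assessments and the Day 1 QOL questionnaire, and other V2 assessments dated on the first-dose date, are taken as pre-dose and may serve as baseline unless documented as taken after the first dose.

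Add a note in the SAP that this clarifies Protocol 18.3. The wording then agrees with SAP 6.3.3. The existing Cycle 2 fallback can stay as it is.

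The cost is one sentence and one note, made before the SAP is finalised ahead of database lock. No new data are needed. The downside is that a few untimed V2 values may in fact have been taken shortly after the first dose.

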10.1.1. Study Visits

The study will consist of a Screening visit on Day -2 (± 1), Baseline visit on Day 1 (if applicable, the Screening and Baseline visits can both be done on Day 1), Phone contacts on Days 3, 5 and 7 (± 1), a TOC visit 14 (± 3) days after Baseline, FU visits at: 14 (± 3) days after EOT, 30 (± 4) after Baseline, 30 (± 4) after EOT and 60 (± 4) days after EOT.

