11.2. Exclusion Criteria

A subject will be excluded from participation in the study if she meets any of the following exclusion criteria:

1) Subject has any vaginal condition other than VVC that may interfere with the diagnosis or evaluation of response to therapy, such as concurrent causes of vulvovaginitis and/or cervicitis including bacterial vaginosis, *Trichomonas*, *Herpes* virus, *Neisseria gonorrhoeae*, *Chlamydia*, symptomatic human papillomavirus infection, or other mixed infections.

- 2) Subject received systemic and/or topical vaginal antifungal treatment, including prescription or over-the-counter products, within 7 days prior to the Screening visit. **Note: The screening visit may be rescheduled if required.**
- 3) Subject is receiving or anticipates requiring treatment with the prohibited medications within the specified timeframes per Appendix I.
- 4) Subject has active menstruation at the Screening visit. Note: **The Screening visit may be rescheduled if required.**
- 5) Subject has a history of or an active cervical/vaginal cancer.
- 6) Subject has a known hypersensitivity to any of the components of the formulation.
- 7) Subject has participated in any other investigational study within at least 30 days (or 5.5 half-lives of the investigational product) before signing the ICF.
- 8) Subject has received prior treatment with ibrexafungerp.
- 9) Subject has any other condition or laboratory abnormality (such as severe hepatic impairment) that, in the judgment of the investigator, would put the subject at unacceptable risk for participation in the study or may interfere with the assessments included in the study.
- 10) Subject is unlikely to comply with protocol requirements.

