14.7. Safety Laboratory Tests

Safety laboratory tests will be performed by a qualified local laboratory. Samples for safety laboratory tests will be collected at the Screening, TOC, and at any unscheduled visit, if needed. If indicated, these may be done more frequently as follow up to a laboratory abnormality.

The following laboratory parameters will be determined:

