15. STUDY SCHEDULE

Detailed schedules of all study visits and procedures are presented in Schedule of Visits and Procedures ([Table 1](#)).

The actual visits will be dependent on the Dosing Group i.e there may be overlapping visits.

Subjects entering Treatment Cycle 2, will follow the same Schedule of Visits and Procedures, starting with Baseline visit and may have visits that are Not Applicable during Treatment Cycle 1.

Table 1: Schedule of Visits and Procedures (Study SCY-078-307b)

Visit	V1 Screening ^a	V2 Baseline ^a	At Home	V3 TOC	V4 FU	V5 FU	V6 FU	V7 FU	Unscheduled Visits ^b
Day (allowable window)	Day -2(±1)	Day 1	Days 2-7	14 ±3 days post Baseline	14 ±3 days post EOT	30±4 days post Baseline	30 ±4 days post EOT	60 ±4 days post EOT	
Study Procedures									
Informed consent	X								
Enrollment and assignment of Subject ID number	X								
Inclusion/exclusion criteria ^c	X	X							
Medical history and demographics	X								
Abbreviated physical exam	X			X					If needed
Vital Signs ^k	X	X		X					If needed
Urine pregnancy test ^c	X			X					If needed
Safety laboratory blood tests ^d	X			X					If needed

Visit	V1 Screening ^a	V2 Baseline ^a	At Home	V3 TOC	V4 FU	V5 FU	V6 FU	V7 FU	Unscheduled Visits ^b
Day (allowable window)	Day -2(±1)	Day 1	Days 2-7	14 ±3 days post Baseline	14 ±3 days post EOT	30±4 days post Baseline	30 ±4 days post EOT	60 ±4 days post EOT	
Rating of vulvovaginal symptoms by the Subject^e	X	X	X	X	X	X	X	X	If needed
Vaginal Examination and rating of vulvovaginal signs by the Investigator^e	X			X	X	If symptoms	If symptoms	If symptoms	If needed
Vulvovaginal sample for other pathogens^e	X			If needed	If needed	if needed	If needed	If needed	If needed
Vulvovaginal sample for KOH and pH^e	X			If symptoms	If symptoms	If symptoms	If symptoms	If symptoms	If needed
Vulvovaginal sample for fungal culture^e	X			X	X	If symptoms	If symptoms	If Symptoms	If needed
Quality of Life Questionnaire		X		X	X	X	X	X	
Study drug dosing		X	X						
Study drug container(s) collection and subject data reviewed				X					
Phone Contact^h			X						
Prior and concomitant medication reviewⁱ	X	X	X	X	X	X	X	X	X
AE monitoring^j	X-----X				X	X	X	X	X

Abbreviations: AE = adverse event; D = day; TOC = test of cure; V = visit; FU = follow up

- a) Screening and Baseline may occur on the same day.
- b) Unscheduled visits can occur if the investigator determines there is a need for one outside of the scheduled per protocol visits.

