6.6.2. Clinical Laboratory Assessments

Laboratory data will be presented as per the international system of units, universally abbreviated as SI (from the French ‘system international’).

Hematology and blood chemistry will be summarized using descriptive statistics by treatment group and visit. Change from baseline values will be summarized similarly by treatment group for each post-baseline scheduled visit. Number and percentage of subjects with urine pregnancy test will be provided by treatment group and visit.

Shift tables from baseline to post-baseline for hematology and blood chemistry assessment, describing shifts to abnormality (low, normal, or high), will be provided. The number of subjects with a non-missing result at both baseline and a specific post-baseline scheduled visit will be used as denominator for that post-baseline scheduled visit.

Separate listings of all hematology, blood chemistry and urine pregnancy data will be provided. In addition, separate listings for hematology, blood chemistry, and urine pregnancy data will be provided for each parameter where a subject had at least one abnormal result.

All laboratory tests required at screening and/or baseline only will be listed.

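### Cycle 2 laboratory results are compared with a value taken after Cycle 1 drug, and no planned summary shows the change from before the first dose

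*SAP*

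**What the plan says.** Protocol 14.7 sets the laboratory schedule: "Samples for safety laboratory tests will be collected at the Screening, TOC, and at any unscheduled visit, if needed". Table 1 agrees. Blood tests are marked at Screening and TOC, not at Baseline and not at any follow-up visit. For re-treatment, Protocol section 15 says: "Subjects entering Treatment Cycle 2, will follow the same Schedule of Visits and Procedures, starting with Baseline visit". Screening is not repeated.

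SAP 6.1.1 resets the reference values for the second cycle: "Baseline values will be re-calculated in Cycle 2 for QOL scale, VVS composite score, physical examinations, lab results and vital signs". It then gives the fallback: "If above baseline value is not available in Cycle 2, then use the last available value in Cycle 1 as baseline for Cycle 2". Protocol 18.3 has a single definition and no reset: "Baseline is defined as the last non-missing assessment prior to the date (and time if appropriate) of the first dose of study drug".

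SAP 6.6.2 plans observed values and changes from baseline by treatment group and visit, listings of all values, and shift tables: "Shift tables from baseline to post-baseline for hematology and blood chemistry assessment, describing shifts to abnormality (low, normal, or high), will be provided". It does not mention Cycle 2 or say which baseline applies there.

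Table 1 also marks a review of the inclusion and exclusion criteria at Baseline, the visit at which Cycle 2 begins. Exclusion 8 in Protocol 11.2 reads: "Subject has received prior treatment with ibrexafungerp".

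**The concern.** The fallback in SAP 6.1.1 is worded as an exception for a missing value. For laboratory tests it is the usual case, because nothing is scheduled that would supply a Cycle 2 value. The reference for Cycle 2 is then a measurement already exposed to study drug, which departs from the protocol's definition.

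Cycle 2 allows up to 14 further days of dosing after 1, 3 or 7 days, so the longest cumulative exposures in the trial are found among these subjects. They are where a laboratory effect that builds up with dosing would be looked for. The planned tables split that effect at Cycle 1 TOC and never add the two parts together.

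The entry passages also do not fit. Every Cycle 2 subject has received ibrexafungerp, so every one would meet exclusion 8 if the Baseline eligibility review were applied as written.

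**Working it through.** The documents give no figure to reproduce here. The check traces the schedule and then does visit-window arithmetic.

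**Inputs**
- TOC and first follow-up timing (Protocol 10.1.1): "a TOC visit 14 (± 3) days after Baseline, FU visits at: 14 (± 3) days after EOT".
- Last follow-up: 60 ± 4 days after EOT (Protocol 10.1.1).
- Dosing: 1, 3 or 7 days in Cycle 1, up to 14 in Cycle 2 (Protocol 12.1).
- Cycle 2 entry: after insufficient improvement at TOC or at the EOT+14 visit (Synopsis), or on a recurrence before the last follow-up visit (Protocol 12.1).
- Assumption: dosing starts on the day of the Baseline visit.

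**Which value becomes the Cycle 2 baseline.** The scheduled draws in Cycle 1 are Screening and TOC. The last is TOC, so unless an unscheduled draw exists, the fallback selects it.

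**Is it free of drug effect?** Count days from Baseline. The last dosing day is d − 1, where d is the number of dosing days, and TOC falls on days 11 to 17. TOC therefore follows the last dosing day by 11 − (d − 1) to 17 − (d − 1) days.

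**How old is it at Cycle 2 entry?** For entry at TOC, 0 days. For entry at EOT+14, nominally (d − 1 + 14) − 14 = d − 1 days. For a recurrence, the upper bound is the last follow-up visit: nominally (d − 1 + 60) − 14, and at the window limits (d − 1 + 64) − 11.

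| Cycle 1 arm | Days from last dosing day to TOC | Age at EOT+14, nominal | Age at last FU, nominal | Age at last FU, window limit | Maximum total dosing days |
|---|---|---|---|---|---|
| 1 day | 11–17 | 0 | 46 | 53 | 1 + 14 = 15 |
| 3 days | 9–15 | 2 | 48 | 55 | 3 + 14 = 17 |
| 7 days | 5–11 | 6 | 66 − 14 = 52 | 70 − 11 = 59 | 7 + 14 = 21 |

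**What the Cycle 2 tables lose.** Let S be the pre-drug value, T1 the Cycle 1 TOC value and T2 the Cycle 2 TOC value. The plan reports T2 − T1. The cumulative change is T2 − S. The difference between them is T1 − S, which is exactly the Cycle 1 change. An illustration with assumed values (upper limit 40, S = 30, T1 = 55, T2 = 90):
- Cycle 1 table: 55 − 30 = +25, normal to high.
- Cycle 2 table as planned: 90 − 55 = +35, high to high.
- Against the pre-drug value: 90 − 30 = +60, normal to high.

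**How much rests on the Cycle 2 TOC value.** With 14 days of Cycle 2 dosing, the last dosing day is day 13 of that cycle. TOC then falls between 11 − 13 = −2 and 17 − 13 = +4 days from it. No later blood test is scheduled, so T2 is normally the only Cycle 2 value, and its reference decides what the table shows.

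**Late recurrence.** Here the reference is old as well as post-drug. A change arising between Cycle 1 TOC and Cycle 2 entry would be counted as a Cycle 2 change. This is misattribution, the opposite of a change dropping out.

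**The case against.** The strongest reply is that a cycle-specific baseline is a recognised choice and that little is concealed. Much of this stands. In the illustration, the move from normal to high appears in the Cycle 1 shift table. SAP 6.6.2 lists all values and separately lists parameters with any abnormal result, and SAP 6.7 provides a profile for every subject. Protocol 16.1 makes any clinically significant laboratory abnormality an adverse event. Safety is descriptive throughout. A reader might infer that a laboratory signal is hidden, but the documents do not support that. What is missing is the cumulative summary.

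A reader might also infer that no laboratory result precedes Cycle 2. That is wrong: the Cycle 1 TOC draw does, it coincides with entry on one route, and Protocol 14.7 allows further draws when needed.

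A third tempting inference is that setting exclusion 8 aside also removes exclusion 9, which covers laboratory abnormalities in the investigator's judgment. The text does not say so. Protocol 12.1 expressly permits Cycle 2, on the investigator's recommendation and after discussion with the sponsor. The documents leave open which criteria are re-checked, and only that can be claimed.

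Finally, Cycle 2 lasts up to 14 days. A short second cycle after 1-day dosing can total less than the 7-day arm, so not every Cycle 2 subject has a long exposure.

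None of this answers the remaining point. Even a fresh draw at Cycle 2 entry would be taken after Cycle 1 drug, so a table built on the re-calculated baseline still could not show the change from before treatment.

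**Conclusion.** The point holds as a gap in the safety tabulation and an unexplained departure from Protocol 18.3. For laboratory tests, the Cycle 2 baseline is normally the Cycle 1 TOC value. It is post-drug in every arm and between 0 and 52 days old nominally (59 at the window limits) in the 7-day arm. The Cycle 2 change differs from the cumulative change by exactly the Cycle 1 change, and a value that was already high and rises further is shown as no shift. No planned summary covers the whole exposure, which can reach 21 days.

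This assumes that no unscheduled draw supplies a later value and that the Cycle 2 tables use the baseline re-calculated in SAP 6.1.1, since SAP 6.6.2 is silent. The documents do not give the number of subjects entering Cycle 2, so the share of laboratory data affected cannot be calculated. The illustrative values say nothing about the likely size of any real effect.

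**What to change.** In SAP 6.1.1 and 6.6.2, report Cycle 2 laboratory changes and shifts against the last value before the first-ever dose, in line with Protocol 18.3. Keep the re-calculated Cycle 2 baseline as a supplementary column, and state in 6.6.2 that Cycle 2 results are tabulated this way. This uses data already collected. The cost is one extra column in the Cycle 2 tables.

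Separately, reconcile three passages: SAP 6.1.1, which expects a Cycle 2 laboratory baseline; Table 1 and section 15 of the protocol, which schedule none and mark an eligibility review at Baseline; and exclusion 8 in Protocol 11.2, which every Cycle 2 subject would meet. How they are reconciled is for the sponsor and investigators to decide. No monitoring or eligibility rule is proposed here.
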